### 12.1.6 Statistical Hypothesis Testing and Control of Multiplicity

Statistical hypothesis testing for lesion count analyses will use the statistical model introduced in Section 12.1.4 and employs the methods of Section 12.1.9 regarding missing values. The analysis of the dichotomized Evaluator’s Global Severity Score will be based on the logistic regression with factors of treatment group and analysis center and employs the methods of Section 12.1.9 regarding missing values.

The overall Type I error will be controlled by requiring the three co-primary efficacy endpoints to be statistically significant. Specifically, failure of any one of the primary efficacy endpoints will invalidate the statistical significance of the secondary efficacy endpoints.

The following stepwise process will be conducted for testing the secondary efficacy endpoints in order to control for multiplicity. These tests will be performed for only the ITT population. The testing process will terminate whenever a statistical test for a step is not significant. All subsequent tests for the remaining steps will be considered not significant. The order of testing is:

Step Number	Secondary Endpoint
1	Percent change in non-inflammatory lesion count from Baseline to Week 12
2	Percent change in inflammatory lesion count from Baseline to Week 12
3	Percentage of subjects who have at least a 2 grade reduction at Week 12 from Baseline in the Evaluator’s Global Severity Score
4	Percent change in non-inflammatory lesion count from Baseline to Week 8
5	Percent change in inflammatory lesion count from Baseline to Week 8
6	Percent change in non-inflammatory lesion count from Baseline to Week 4
7	Percent change in inflammatory lesion count from Baseline to Week 4

The following stepwise process will be conducted for testing the supportive efficacy endpoints in order to control for multiplicity. These tests will be performed for only the ITT population. In order to control for multiplicity, failure of any one of the secondary efficacy endpoints will invalidate the statistical significance of the supportive efficacy endpoints. The testing process

will terminate whenever a statistical test for a step is not significant. All subsequent tests for the remaining steps will be considered not significant. The order of testing is:

Step Number	Supportive Endpoint
1	Percent change in non-inflammatory lesion count from Baseline to Week 2
2	Percent change in inflammatory lesion count from Baseline to Week 2
3	Percentage of subjects who have at least a 2 grade reduction at Week 8 from Baseline in the Evaluator's Global Severity Score
4	Percentage of subjects who have at least a 2 grade reduction at Week 4 from Baseline in the Evaluator's Global Severity Score
5	Percentage of subjects who have at least a 2 grade reduction at Week 2 from Baseline in the Evaluator's Global Severity Score

### 12.1.7 Descriptive Statistics

Descriptive statistics will be presented for the following parameters by treatment group for both the ITT and PP populations:

- Frequency and percent distributions of the Evaluator's Global Severity Score at Baseline and Weeks 2, 4, 8, and 12.
- Frequency and percent distributions of the dichotomized Evaluator's Global Severity Score at Baseline and Weeks 2, 4, 8, and 12.
- Descriptive statistics including mean, median, standard deviation, minimum, and maximum will be used to summarize inflammatory and non-inflammatory lesion counts at Baseline and Weeks 2, 4, 8, and 12.
- Descriptive statistics including mean, median, standard deviation, minimum, and maximum will be used to summarize the absolute and percent change in inflammatory and non-inflammatory lesion counts at Weeks 2, 4, 8, and 12.

### 12.1.8 Pooling Analysis

The clinical study will be conducted under a common protocol for each investigational site with the intention of pooling the data for analysis. Every effort will be made to promote consistency in study execution at each investigational site. The study is intended to be conducted in a manner such that a minimum of 5 subjects will be enrolled in each treatment arm for any investigator. In the event that there are too few subjects in a treatment arm for an investigator, then this investigator's data will be combined, within geographic region, to achieve the desired sample size minimum per arm. The combining of investigator's data will be accomplished by taking the investigator with the smallest enrollment and combining it with the investigator with the largest

enrollment. If there is a further need to combine data, then the data of the investigator with the second smallest enrollment will be combined with the investigator's data which had the second largest enrollment, and so on. This process will continue for all investigators who did not have a minimum of 5 subjects per treatment arm. The process of combining investigator data that have insufficient subjects per treatment arm will result in redefining the groups of investigators for the purposes of statistical analyses. These combined groups will be referred to as "analysis centers" in the statistical analyses based on ANCOVA and stratified logistic testing.

Prior to investigating the treatment effect within the analysis centers, the magnitude of the site main effect will be investigated to determine if the main site-to-site variability is such that it could mask the analysis center effects. Thus, prior to pooling, the lesion count data at Week 12 will be analyzed with an ANCOVA with factors of treatment group, site, and the interaction term of treatment group by site and also the percent of subjects with treatment success at Week 12 will be analyzed with a logistic regression with factors of treatment group, site, and the interaction term of treatment group by site. If these analyses are not computationally feasible due to some sites having very few subjects enrolled, the low enrolling sites will be excluded from these analyses.

The consistency of treatment response will be investigated across the analysis centers subsequent to combining the data as described above. Statistical tests will be conducted to identify if there are extreme analysis centers that could affect the interpretation of common statistical and clinical conclusions. An analysis center by treatment interaction will be included in the primary variable analyses to test for parallel treatment effect at an alpha level of 0.10. Change from baseline in inflammatory lesions and non-inflammatory lesions will be analyzed with an ANCOVA (unranked or ranked) with factors of treatment, analysis center, and treatment by analysis center interaction and the respective baseline lesion count variable as a covariate. For the purpose of testing consistency of treatment response, the dichotomized EGSS will be analyzed with a logistic regression procedure with factors of treatment, analysis center, and treatment by analysis center interaction. Further examination will follow for any variables that have a significant ANCOVA or logistic regression interaction term. In the event that the ANCOVA or logistic regression interaction (referred to henceforth as the "appropriate test") p-value is less than or equal to 0.10, a sensitivity analysis that excludes analysis centers with the extreme efficacy result will be performed to determine the robustness of the treatment effect. On the other hand, if the outcome of the appropriate test has a p-value greater than 0.10, then the conclusions from the pooled data will be considered to be free of the impact of extreme analysis centers.

The first step in conducting a sensitivity analysis is to identify the extreme analysis center or centers that contribute to the statistical significance of the appropriate test. The process involves submitting subsets of analysis centers to the appropriate test and observing the appropriate test p-value for the subset. Subsets with p-values greater than 0.10 for the appropriate test are considered homogeneous.

The search for an extreme analysis center begins by analyzing all subsets that can be created by excluding one analysis center. If one or more of the subsets result in an appropriate test p-value greater than or equal to 0.10, then the analysis center excluded from the subset with the largest p-value for the appropriate test is deemed to be the extreme analysis center.

If all appropriate test subset p-values are less than or equal to 0.10, then the process will analyze the appropriate test for all subsets that can be created by excluding two analysis centers. If one or more of these subsets generate appropriate test p-values larger than 0.10, then the analysis centers excluded from the subset with the largest appropriate test p-value are deemed the extreme analysis centers.

Thus, the process of identifying the extreme analysis centers will continue in a stepwise manner by first excluding one, then two, then three, etc., analysis centers until the appropriate test p-value exceeds 0.10.

Once the extreme analysis center or centers have been identified, then the treatment p-values of the remaining analysis centers will be computed. Inferences will be drawn from the treatment p-value, as well as any pertinent observations regarding the extreme analysis center or centers.

Additionally, it is noted that this process excludes subjects from the analysis in a non-random manner and has an unpredictable impact on the power of the treatment effect test. In the event that the treatment effect of the remaining subset is not statistically significant, due consideration of the post-hoc aspects of the process will be given when the results are interpreted. Conclusions will be presented by the sponsor as appropriate to the findings of the sensitivity analysis.

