## 12 Statistics

All statistical processing will be performed using SAS® version 9.3 or later unless otherwise stated. Statistical significance will be based on two-tailed tests of the null hypothesis resulting in p-values of 0.05 or less.

The primary method of handling missing efficacy data will be based on estimation using the method of Markov Chain Monte Carlo (MCMC) imputation. This method provides robust estimation when the pattern of missingness is arbitrary. Additionally, the estimation will be done

for each treatment group separately so that the pattern of missingness for one group does not influence the estimation of missing data for another group. Groups of complete datasets following the estimation will be concatenated to form analysis datasets for the comparative analyses and subsequent imputation result inference with SAS PROC MIANALYZE. Descriptive statistics will also be derived from the multiply imputed datasets.

Additionally, a model-based multiple imputation process will be used as a sensitivity analysis to the MCMC imputation. The absolute change in lesion count will also be analyzed using a repeated measures ANCOVA for lesion count data or a repeated measures logistic regression model (generalized estimating equations) for the dichotomized EGSS. Finally, a tipping point analysis will be performed for the primary endpoints.

A statistical analysis plan (SAP), describing all statistical analyses will be provided as a separate document. The SAP will be finalized prior to unblinding of the study treatments.

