### **12.8.2 Sample Size Determination**

These power calculations are based primarily on the observed Week 12 results of the Phase 2 study, V01-120A-201. This study was a four-arm trial including IDP-120 Gel versus its individual gel components and Vehicle Gel and is therefore a relevant study for powering the current study.

A sample size of 300 per treatment arm has greater than 99% power to detect a statistically significant difference in non-inflammatory lesions with a significance level of 0.05. The estimated absolute change from baseline in treatment means were 13.3 and 8.7 for IDP-120 Gel versus its Vehicle gel, respectively, with a standard deviation of 11.0.

A sample size of 300 per treatment arm has greater than 99% power to detect a statistically significant difference in non-inflammatory lesions with a significance level of 0.05 using the estimated absolute change from baseline in treatment means of 18.8 and 7.8 for IDP-120 Gel versus its Vehicle Gel, respectively, with a standard deviation of 16.4.

In order to achieve at least 95% power to detect a statistically significant difference in the percentage of subjects who have at least a 2 grade reduction at Week 12 from Baseline in EGSS and are Clear or Almost Clear with a significance level of 0.05, a sample size of 293 per treatment group is required. The estimated percentages with a 2 grade reduction at Week 12 from Baseline in the EGSS and Clear or Almost Clear are 26.6% and 14.3% for IDP-120 Gel versus its Vehicle Gel respectively. For simplicity, a sample size of 300 per treatment arm will be used.

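### The EGSS treatment-by-center check in section 12.1.8 has error rates far from its nominal 10% if analysis centers stay near the planned 24-35, so its all-clear and its exclusion trigger are unreliable; the primary EGSS test is not affected

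*Combined protocol and SAP*

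**What the plan says.** Section 12.1.8 (Pooling Analysis) aims for enrolment such that "a minimum of 5 subjects will be enrolled in each treatment arm for any investigator". Investigators below that number are merged into analysis centers. The rule counts subjects and sets no minimum number of successes.

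To check consistency, "the dichotomized EGSS will be analyzed with a logistic regression procedure with factors of treatment, analysis center, and treatment by analysis center interaction". The interaction is used "to test for parallel treatment effect at an alpha level of 0.10". Two outcomes follow:

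- If p > 0.10, the "conclusions from the pooled data will be considered to be free of the impact of extreme analysis centers".
- If p is 0.10 or less, a sensitivity analysis removes extreme centers. They are found by rerunning the same test on subsets that leave out one center, then two, and so on.

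The section does not say whether the p-value is Wald, likelihood-ratio, score or exact, and it names no penalised method. Its one rule for infeasible fits concerns the site-level models run before pooling.

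Section 12.8.2 expects EGSS success of "26.6% and 14.3% for IDP-120 Gel versus its Vehicle Gel respectively". Section 7.1 plans about 24-35 centers.

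**The concern.** The interaction model estimates a separate treatment effect in each analysis center. In a center where one arm has no successes, that effect has no finite maximum-likelihood estimate. Elsewhere it rests on one to three successes per arm. Large-sample approximations for the interaction test are poor in such data, and the two usual logistic tests err in opposite directions.

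The plan turns this p-value into a firm decision. A test that hardly ever rejects makes the all-clear close to automatic. A test that rejects too often starts an exclusion search in trials with no heterogeneity. The choice between them is left open. At stake is what the report may say about consistency across centers for one of three co-primary endpoints.

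**Working it through.** **Inputs.** Success 26.6% active and 14.3% vehicle, 300 per arm (12.8.2); interaction alpha 0.10 and at least 5 per arm per analysis center (12.1.8); 24-35 sites (7.1). The number of analysis centers after pooling, K, is not given, so 6 to 35 was examined.

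**The plan's own figure first.** Section 12.8.2 says that "a sample size of 293 per treatment group is required" for at least 95% power. With two-sided alpha 0.05 and pooled rate 0.2045:

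- n' = [1.960 × √(2 × 0.2045 × 0.7955) + 1.645 × √(0.266 × 0.734 + 0.143 × 0.857)]² / 0.123² = 276.5
- with continuity correction, n = (n'/4) × [1 + √(1 + 4/(n' × 0.123))]² = 292.5, which rounds up to 293.

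The stated figure is reproduced, so the rates are used as the plan uses them.

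**Cell sizes.** 300/35 = 8.6 and 300/24 = 12.5 subjects per arm per center. Expected successes per vehicle cell are 8.6 × 0.143 = 1.2 to 12.5 × 0.143 = 1.8, and per active cell 8.6 × 0.266 = 2.3 to 12.5 × 0.266 = 3.3.

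**Chance of no successes in a cell of m subjects, (1 − p)^m:**

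| m | Vehicle, 0.857^m | Active, 0.734^m |
|---|---|---|
| 5 | 46% | 21% |
| 10 | 21% | 4.5% |
| 12 | 16% | 2.4% |

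With 30 equal centers (m = 10), a center has at least one empty cell with probability 1 − (0.786 × 0.955) = 0.249. That gives 30 × 0.249 = 7.5 such centers on average, and P(at least one) = 1 − 0.751^30, about 99.98%. The same calculation gives 3.9 centers and 98.6% at K = 24, and about 11 centers and more than 99.99% at K = 35.

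**The tests compared, each on K − 1 degrees of freedom:**

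- Likelihood ratio: twice the log-likelihood gain of the interaction model over treatment plus center.
- Wald: Σ w_k(θ_k − θ̄)², where θ_k is the center log odds ratio and 1/w_k is the sum of reciprocals of its four cell counts. An empty cell drives w_k to zero, so that center drops out however extreme it is.
- Score (Breslow-Day type): observed against expected successes under one common odds ratio, with no separate fit per center.

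**Rejection at nominal 10% when the odds ratio is truly common** (simulated trials, equal centers):

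| K | Likelihood ratio | Wald |
|---|---|---|
| 35 | 37% | 0.01% or less |
| 30 | 32% | 0.01% or less |
| 24 | 26% | 0.01% or less |
| 20 | 22% | 0.1% |
| 15 | 17% | 1% |
| 10 | 14% | 4% |
| 6 | 11% | 8% |

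The score test rejected in 10.2-11.4% of trials over the whole range of K. Unequal center sizes (smallest 5-6 per arm) gave 26-35% for likelihood ratio and about 0% for Wald. Separate simulations gave 10-12.5% for Breslow-Day with Tarone correction (15-30 centers) and 12-13% for an uncorrected version (24-35 centers).

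**Empty cells are not the whole cause.** At K = 15, in trials with no empty cell, Wald still rejected in only 1.4%.

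**Real heterogeneity, K = 24:**

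| Scenario | Wald | Likelihood ratio | Score |
|---|---|---|---|
| One center, 10/12 active vs 0/12 vehicle | 0% | 88% | 61% |
| A quarter of centers at 60% vs 3% | 0.7% | 99% | 97% |
| A quarter reversed, 10% vs 45% | 27% | 99.8% | 99% |

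With one center at 75% vs 8%, Wald detected it in about 0.1% of trials and Breslow-Day in about 40%.

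**One fitted data set**, 24 centers, one at 10/12 vs 0/12: Wald p = 0.96, likelihood-ratio p = 0.035. The same data would be cleared under one test and sent to the exclusion search under the other. Leaving that center out moves the Wald p-value only to 0.94, so a Wald-based search would not single it out.

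**The case against.** **A reader might infer that the EGSS co-primary result is at risk.** The documents do not support this. Sections 12.1.5, 12.1.6 and 12.1.9 give the EGSS model as treatment and analysis center only. The rule in 12.1.4 that keeps a significant interaction in the model belongs to the lesion-count ANCOVA.

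**A reader might infer that centers are removed from the main analysis.** Section 12.1.8 calls the exclusion step a sensitivity analysis and itself warns that exclusion is non-random, affects power unpredictably and is post hoc. A check of 1,500 null trials with 24 equal centers shows how little a false trigger may change. The likelihood-ratio test triggered in 420, and dropping one center ended the search in 279. Of the 270 of these that were significant beforehand, 12 lost significance: 12/270 = 4.4%, or 12/1,500 = 0.8% of all trials. The 141 trials needing two or more exclusions were not examined.

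**The separate SAP may settle the statistic.** Section 12 announces such a document, and a score, exact or penalised test would fit the wording of 12.1.8. The text reviewed has no such detail. The sentence that reads p > 0.10 as an all-clear would need changing under any statistic.

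**Heavy pooling would shrink the problem.** It would: at 6 centers the rates are 11% and 8%. But only investigators below 5 per arm are merged, so pooling that heavy is not implied.

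These points limit the consequence. They do not restore the error rates of the check.

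**Conclusion.** The concern holds for the consistency check. If analysis centers number about 24-35, the rule triggers in about 26-37% of homogeneous trials under likelihood ratio, which is 2.6 to 3.7 times the nominal rate, and in about 0% under Wald. At 15 centers the rates are about 17% and 1%, and at 10 about 14% and 4%. Small cells in general, as well as empty ones, drive the Wald conservatism.

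This rests on the plan's own success rates, 300 per arm, and an assumed number of analysis centers. It describes error rates. A reader might infer that the rule gives a wrong answer in every data set, and the calculations do not show that. What is affected is the homogeneity statement and the exclusion sensitivity analysis for EGSS.

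**What to change.** 1. For the EGSS consistency check and its subset search, replace the logistic interaction p-value with a test suited to sparse stratified tables, such as Breslow-Day with Tarone correction or the exact Zelen test, stratified by analysis center at 0.10. The Zelen test was not computed here.
2. State how the test is applied with imputed data: for example, on observed Week 12 data, or in each of the 5 imputed data sets with a combining rule fixed in advance.
3. Replace the all-clear sentence with wording such as *no evidence of heterogeneity was found*, and read it beside success differences by analysis center. Section 12.8.4 already plans site-specific summaries, so this extends an existing output.

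The cost is a wording change and one standard procedure, settled before unblinding, with no added subjects, visits or data. The replacement is not covariate-adjusted, but the EGSS model in 12.1.8 has no covariate beyond center. Its power is limited: about 40% for one center at 75% vs 8% among 24. That is a further reason not to read p > 0.10 as proof that no center is extreme.

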### **12.1.9 Missing Efficacy Data Imputations**

#### *Lesion Count Variable Missing Data Imputation*

Missing 12 week data will be estimated by multiple imputation and subsequently analyzed. Missing lesion count data will be derived for the analysis using the method of MCMC multiple imputation which does not rely on the assumption of data missing at random. Additionally, the pattern of missing observations in each treatment group cannot influence the missing value estimation in the other because the imputation is being conducted independently for each treatment group.

Multiple imputation and subsequent analysis will involve 3 distinct phases with these principal tasks:

1. Create a data set of subjects, one for each treatment group, with observed values and those needing estimation by MCMC. The missing lesion count values in each data set will be filled in using the MCMC method 5 times to generate 5 data sets. The resulting data sets for each treatment arm will be combined into one complete data set for each imputation.

**Syntax:**

```
proc mi data=datain out=dataout seed=&seed. nimpute=5<options>;
  where trtpn=(1, or 2);
  mcmc chain=multiple;
  var baseline week2 week4 week8 week12;
  run;
```

2. For each complete data set, the absolute change in lesion counts will be computed. Each complete data set will be analyzed as specified for the particular analysis.
3. The results from these analyses will be combined into a single inference using SAS PROC MIANALYZE.

A total of 4 random seeds will be needed to impute inflammatory lesion counts and non-inflammatory lesion counts for the two treatment groups. Those 4 random seeds have been pre-specified by using a random number generator:

- Inflammatory Lesion Counts; IDP-120 Gel: Seed= 34116691
- Inflammatory Lesion Counts; IDP-120 Vehicle: Seed= 1806432384
- Non-Inflammatory Lesion Counts; IDP-120 Gel: Seed= 2049678471
- Non-Inflammatory Lesion Counts; IDP-120 Vehicle: Seed= 655282615

